4.10.3.5 Analysis of Overall Survival

OS will be summarized descriptively and graphically using Kaplan Meier methods. The Kaplan Meier survival estimates, together with the number of subjects, percentage of subjects to experience the event,

[name] S.A	
Protocol RI-01-006	

and the number and percentage of subjects censored will be summarized by treatment group. If data warrant, the Kaplan-Meier estimate for the median overall survival time and the first and third quartiles will be determined along with 95% CIs using the Brookmeyer-Crowley method.

A by-subject listing will be provided for OS by treatment group.

If a subject is not known to have died at the time of analysis cut-off, OS will be censored at the date of last contact. For example, if information of death is still pending or unknown under clinical operation and could not be obtained this information during the dry run analysis, then the last contact date will be considered as censored date of overall survival analysis. For the Week 28 CSR analysis, subjects will be administratively censored at Week 28 if no death or other censoring appeared prior to Week 28.

4.10.3.6 Analysis of Duration of Response by Central Review

Duration of response (DOR) by central review is defined as the time from date of the first documentation of tumor response (CR, CRu or PR) to the date of first documentation of PD or to death due to any cause up to 52 weeks/EOS. Subjects continuing without PD or death due to underlying cancer will be censored at the date of their last adequate tumor assessment using the event/censoring rules described for PFS analysis, see Table 11. For the Week 28 CSR analysis, DOR data until a cutoff date not earlier than the date of the latest Week 28 evaluation conducted for any study subject will be included in the analysis. Additionally, DOR data will also be summarized for all subjects based on their Week 28 visit cut date.

DOR will be summarized descriptively and graphically using Kaplan Meier methods. The Kaplan Meier survival estimates, together with the number of subjects, percentage of subjects to experience the event, and the number and percentage of subjects censored will be summarized by treatment group. If data warrant, the Kaplan-Meier estimate for the median duration of response time and the first and third quartiles will be determined along with 95% CIs using the Brookmeyer-Crowley method. The interpretation of results for DOR is limited as DOR is only defined for subjects with a tumor response CR, CRu or PR.

A by-subject listing will be provided for central review and investigator assessed DOR by treatment group.

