2.2.2 Follicular Lymphoma

CD-20 positive, B-cell NHL is a heterogeneous group of malignancies with varying clinical outcomes.⁶ The risk of mortality from NHL depends on whether it is indolent or aggressive; indolent forms of NHL, such as follicular lymphoma (FL), have significantly better prognosis than more aggressive forms like diffuse large B-cell lymphoma (DLBCL) and mantle cell lymphoma.

Follicular lymphoma is the most common subtype of indolent NHL in the Western Hemisphere. With current therapy options, prognosis is favourable, with median overall survival (OS) exceeding 12 years. Recent advances in disease management and our understanding of the biology of FL have led to a dramatic change in the treatment landscape. Despite this progress, FL remains incurable with standard therapies.⁷

Tumour grade is used to classify FL based on the number of centroblasts per high-power field (HPF). In general, cases harbouring a greater number of centroblasts behave more aggressively and are associated with a higher risk of transformation to DLBCL. Grade 1 (<5 centroblasts/HPF) and Grade 2 (6 to 15 centroblasts/HPF) FL are combined in the World Health Organisation (WHO) classification given their similar clinical behaviour. Grade 3 FL can be further subdivided into 3a and 3b, with the latter distinguished by a lack of centrocytes. Despite a higher tumour grade, FL Grade 3a behaves like Grade 1-2 FL and as such should be approached in a similar fashion. FL Grade 3b represents a distinct entity characterised by a diffuse architectural pattern, frequent loss of CD10 expression, and absence of t (14;18) chromosomal translocation. Consequently, its clinical course and treatment mirror that of DLBCL.⁷ Subjects with Ann Arbor Stage II, III or IV of histological Grade 1, 2, or 3a with at least one measurable lesion (Section 10.1.14), will be enrolled in this study.

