3.2.1.2 Definition of Secondary Efficacy Endpoints / Variables

Secondary efficacy endpoints / variables are:

• Overall response (of either CR, CRu or PR) at Week 12 and overall response (of either CR, CRu or PR) at Week 28 based on central radiology review applying the Cheson 1999² response criteria for malignant lymphoma

[name] S.A	
Protocol RI-01-006	Statistical Analysis Plan

- Complete Response (CR) at Week 28 based on central radiology review applying the Cheson 1999² response criteria for malignant lymphoma
- Complete Response (CR) as best response up to Week 28 (derivation similar to primary endpoint, BOR) based on central radiology review applying the Cheson 1999² response criteria for malignant lymphoma
- Duration of response (DOR) based on central radiology review applying the Cheson 1999² defined as time from date of the first documentation of tumor response (CR, CRu or PR) to date of first documentation of PD or to date of death due to any cause (whatever is first) up to Week 52 / EOS + 1
- Progression-free survival (PFS) by central review applying the Cheson 1999² progression criteria for malignant lymphoma is defined as the time from date of randomization to the date of documented PD (PD from imaging shared through central imaging data or eCRF early termination page) or death due to any cause up to Week 52 / EOS + 1. PFS censoring rules are defined in Section 4.10.3.1.
- Overall survival (OS) is defined as the time from date of randomization to date of death due to any cause up to Week 52 / EOS + 1. OS censoring rules are defined in Section 4.10.3.5.

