4.10.3.1 Analysis of Progression Free Survival by Central Review

PFS (see Section 3.2.1.2) by central review will be summarized descriptively and graphically using Kaplan Meier methods. The Kaplan Meier survival estimates, together with the number of subjects, percentage of subjects to experience the event, and the number and percentage of subjects censored will be summarized by treatment group. If data warrant, the Kaplan-Meier estimate for the median progression free survival time and the first and third quartiles will be determined along with 95% CIs using the Brookmeyer-Crowley method. For the analysis of PFS, the PD assessment by central review will be used to determine the status and date of events for PFS regardless of treatment discontinuation.

[name] S.A	
Protocol RI-01-006	Statistical Analysis Plan

A by-subject listing will be provided for central review as well as investigator assessed PFS by treatment group.

Table 11 provides the detailed event/censoring rules for statistical analysis of PFS.

 Table 11 Event/Censoring Rules for PFS Analysis

Situation	Date	Outcome
No baseline tumor assessment	Date of randomization	Censored
PD or death at or before next scheduled assessment	Date of the first radiological tumor assessment demonstrating PD, or date of death	Progressed
New anticancer treatment started without documented PD	Date of last radiological tumor assessment prior to initiation of new therapy	Censored
PD or death after more than one missing assessments	Date of the last radiological tumor assessment prior to the missing assessments	Censored
No PD and no death	Date of the last radiological tumor assessment	Censored
Death before first PD assessment	Date of death	Progressed
Death between adequate assessment visits	Date of death	Progressed

For the Week 28 CSR analysis, subjects will be administratively censored at Week 28 if no progression or other censoring appeared prior to Week 28.

4.10.3.2 Analysis of Overall Response by Central Review at Week 12 and at Week 28

OR by central review at Week 12 and at Week 28 will be summarized using frequencies, percentages and corresponding 95% CIs by treatment group.

4.10.3.3 Analysis of Complete Response by Central Review at Week 28

Complete response (CR) by central review at Week 28 will be summarized using frequency, percentage and corresponding 95% CI by treatment group.

4.10.3.4 Analysis of Complete Response by Central Review up to Week 28

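### SAP 4.10.3.6 contradicts itself on duration of response: death from any cause is an event by definition, but the censoring sentence recognises only death from the underlying cancer, and the SAP does not say which governs

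*SAP*

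**What the plan says.** The definition is the same wherever it appears. In SAP 4.10.3.6 DOR runs from the first documented response "to the date of first documentation of PD or to death due to any cause up to 52 weeks/EOS". SAP 3.2.1.2 ends it at the "date of first documentation of PD or to date of death due to any cause (whatever is first"). The Protocol synopsis and Protocol sections 3 and 9.4.1.2 agree.

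The second sentence of SAP 4.10.3.6 sets the censoring rule: "Subjects continuing without PD or death due to underlying cancer will be censored at the date of their last adequate tumor assessment". It continues: "using the event/censoring rules described for PFS analysis, see Table 11".

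Table 11, in SAP 4.10.3.1, never mentions cause of death. The rows "Death between adequate assessment visits" and "Death before first PD assessment" are both events at the date of death. The row that censors a subject for having had no event is headed "No PD and no death". Three other rows also censor: no baseline tumour assessment, new anticancer therapy begun before documented progression, and progression or death following more than one missed assessment.

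DOR is reported descriptively by arm: numbers and percentages of events and of censored subjects, Kaplan-Meier estimates and, if the data allow, quartiles. SAP 4.14, which lists changes from the protocol, records no change to the DOR event.

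**The concern.** A censoring rule should be the complement of the event definition. Here it is not. A responder who dies of another cause without progressing is an event in the first sentence of the section and, taken at its word, censored in the second. The same death would be an event for PFS, and the attribution of cause would decide whether a DOR event exists at all.

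The narrower rule could be programmed as written. SAP 4.11.3.2 summarises the primary cause of death, and the EMA intercurrent-event table in SAP 4.10.2.2.2 already separates deaths by reason. Protocol 9.1.3 foresees COVID-19 deaths, so a non-lymphoma death in a responder is a case the plan itself expects to have to handle.

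At stake are the reported event and censoring counts and the Kaplan-Meier curves for a protocol-defined secondary endpoint. If the narrowing is deliberate, it is an undeclared change to that endpoint.

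**Working it through.** **1. The statements side by side.** The plan gives no DOR event count, so there is no stated figure to reproduce. The check is one of wording.

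| Source | Death without PD, not from lymphoma |
|---|---|
| Definition: SAP 3.2.1.2, SAP 4.10.3.6 first sentence, Protocol 3 and 9.4.1.2 | Event |
| SAP 4.10.3.6 second sentence, read literally | Censored at last adequate assessment |
| Table 11, cited in that same sentence | Event at date of death, unless one of the three special censoring rows applies |

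**2. One hypothetical case.** A subject responds at Week 12, is still in response at the Week 28 scan, has missed no scan and had no new therapy, and dies of COVID-19 at Week 40.
- Definition and Table 11: event, DOR = 40 − 12 = 28 weeks.
- Censoring sentence read literally: censored at Week 28, DOR = 28 − 12 = 16 weeks.
- PFS under Table 11: event at Week 40.

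**3. Size, for scale only.** Inputs from the documents:
- 312 subjects (SAP 4.13.2).
- 88% expected reference response rate (SAP 4.10.2.3.4).
- Scans at Weeks 12, 28 and 52.
- For follicular lymphoma in general, "With current therapy options, prognosis is favourable, with median overall survival (OS) exceeding 12 years" (Protocol 2.2.2).

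Assumptions: exponential survival, all responses at Week 12 (so 52 − 12 = 40 weeks at risk), median overall survival between 12 years (the documents' floor) and 40 years, and 50% to 100% of deaths not due to lymphoma.

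Responders: 0.88 × 312 = 274.6. Deaths = 274.6 × [1 − exp(−(ln 2 / median) × 40/52)].

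| Median survival | All-cause deaths, arms pooled | Non-lymphoma deaths, 50% to 100% |
|---|---|---|
| 12 years | 274.6 × 4.35% = 11.9 | 6.0 to 11.9 |
| 20 years | 7.2 | 3.6 to 7.2 |
| 40 years | 3.6 | 1.8 to 3.6 |

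So about 2 to 12 deaths could change status. If responses came at Week 28, leaving 24 weeks, all-cause deaths would be 7.2 (12-year median) or 2.2 (40-year median). With a 77% response rate (the induction-only arm described in Protocol 2.2.3) there would be 240.2 responders and, over 40 weeks, 10.4 or 3.2 deaths.

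**4. Effect on the curve.** This also needs a progression rate, which the documents do not give. With assumed progression p over the 40 weeks, H = (ln 2 / median) × 40/52, and f the non-lymphoma share of deaths:
- All deaths counted: (1 − p) × exp(−H).
- Non-lymphoma deaths censored: (1 − p) × exp(−(1 − f)H).

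| p = 10% | Counted | Censored, f = 50% | Censored, f = 100% | Gap (points) |
|---|---|---|---|---|
| Median 12 years | 0.861 | 0.880 | 0.900 | 1.9 to 3.9 |
| Median 40 years | 0.888 | 0.894 | 0.900 | 0.6 to 1.2 |

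Varying p from 5% to 20% widens the range of gaps only to 0.5 to 4.1 points. These are pooled estimates; nothing here bears on a difference between arms.

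**The case against.** The strongest answer is that the section settles itself. The censoring sentence does not stop at the cause qualifier: it says the censoring follows Table 11, and Table 11 counts deaths whatever their cause. Every statement of the definition says the same. One loose phrase stands alone, and a subject described as continuing can be read as one still alive.

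Much of this stands. A reader might infer from the phrase that non-lymphoma deaths will be censored instead of counted. The documents do not support that, because the operative table points the other way. What remains is that the sentence first says who is censored and then cites the table. One programmer may take the population from the sentence and only the dates from Table 11; another may apply Table 11 in full. Reading the subjects as alive does not rescue the phrase, since the cause qualifier would then have no function.

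A reader might also infer, from an indolent disease followed for a year during a pandemic, that most deaths will not be from lymphoma and that the phrase therefore decides nearly every death. That is plausible, but neither document gives a split by cause or a COVID-19 death rate.

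It is also fair that the consequence is small. DOR carries no test or margin, the SAP itself calls its interpretation limited, and the planned by-subject listings of DOR and deaths would let an affected case be found.

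**Conclusion.** The contradiction is real, and the text is wrong as written. The conflict is unresolved, so it does not establish that any death will be censored. It touches one descriptive secondary endpoint. The equivalence decision on best overall response up to Week 28 is unaffected, and PFS and overall survival have their own rules.

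The illustrative size (a handful of deaths, at most about a dozen, and roughly 0.5 to 4 Kaplan-Meier points) rests wholly on the assumptions shown. The upper end needs both the 12-year floor and every death to be unrelated to lymphoma. It should not be read as a forecast. The case for acting is that a stated analysis rule conflicts with the protocol's endpoint definition and costs almost nothing to correct.

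**What to change.** In the censoring sentence of SAP 4.10.3.6, change the cause attached to death from the underlying cancer to any cause. Only responders with neither progression nor death are then censored for lack of an event, and DOR follows its own definition and Table 11. Table 11's other censoring rows (no baseline assessment, new anticancer treatment, more than one missing assessment) continue to apply.

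If a version counting only lymphoma deaths is wanted, add it as a labelled sensitivity analysis. If the narrower event was meant to be the main analysis, it needs to be declared and justified in SAP 4.14.

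The cost is one phrase in the SAP and a check of the DOR programming against it. No new data are needed.

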4.10.3.7 Analysis of Repeat-Bone Marrow Biopsy Data

Bone marrow biopsies or aspirations performed up to 6 weeks prior to the first administration of study drug may be used. Additional bone marrow biopsies are required for any subject who has a response of CR at an evaluation point and either had a bone marrow examination positive for FL at Screening or shows new abnormalities in the peripheral blood counts or blood smear that clinically indicates a bone marrow evaluation is required.

A summary of the number of subjects with repeat-bone marrow results including overall cellularity, tumor cell infiltration at screening and ongoing maintenance treatment period will be summarized by treatment group.

A by-subject listing of bone marrow biopsies will be generated using the including date and time of bone marrow biopsy performed, overall cellularity, tumor cell infiltration: lymphoplasmacytic cell involvement in the marrow, intertrabecular space (0%-100%), general marrow involvement by lymphoma (0%-100%).

4.10.4 Analyses of Exploratory Efficacy Endpoints / Variables

BOR up to Week 28 based on central radiology review based on the Lugano criteria (Cheson 2014¹⁴) will be summarized using frequency and percentage with corresponding 95% CI by treatment group for subjects with PET data in the ITT Analysis Set. A summary of any discrepancies between response designation via the 1999 IWG criteria (primary endpoint) and Lugano criteria will be provided.

[name] S.A	
Protocol RI-01-006	Statistical Analysis Plan

A by-subject listing of the Lugano criteria data will be provided with tumor response assessment at Week 28.

4.11 Safety Analyses

All safety analyses will be based on the SAF.

4.11.1 Analysis of Extent of Exposure

Exposure summary will be based on the actual dose administered [mg] collecting in the eCRF.

Duration of exposure [weeks] = $\frac{\text{last administration date} - \text{first administratin date} + 1}{7}$

Descriptive summaries will be provided for

- duration of exposure by treatment group
- cumulative actual dose by treatment period (induction, maintenance, overall) and treatment group
- cumulative planned dose by treatment period (induction, maintenance, overall) and treatment group
- dose interruptions, missed doses, dose delays and discontinuations by treatment period (induction, maintenance, overall) and treatment group.

A by-subject listing of study drug exposure will be provided, including infusion start date/time, end date/time, medication kit ID, actual administration dose, dose delay, dose reduction, dose interruption, dose not done, reason of not done and infusion-related reaction.

4.11.2 Analysis of Adverse Events

All reported terms for AEs will be coded using the latest version of MedDRA version 21.1 or the latest. Before database lock the latest version of MedDRA will be used to code the AE terms for all study subjects. The US National Cancer Institute (NCI) Common Terminology Criteria for Adverse Events (CTCAE), version 5.0 (NCI-CTCAE version 5.0) will be used by investigator to assess the severity grade of all AEs.

For all AE tables, subjects will be counted once for each MedDRA PT and each SOC. Unless specified otherwise, AEs will be summarized in the alphabetical order of SOC and then decreasing frequency of PT within the SOC for the treatment group. If the frequency of PT within the SOC is tied, PT will be sorted alphabetically. Summaries by PT will be sorted by decreasing frequency according to the "DRL_RI" subject incidence.

TEAEs are defined as any AE occurring or worsening on or after the first dose of study treatment. AEs which are already present before the first study treatment and increase in severity after the first study treatment will be considered as TEAEs. Pre-existing AEs before the first study treatment with no increase in severity after the first study treatment will not be considered as TEAEs.

All treatment-emergent adverse events (TEAEs) will be summarized by SOC, PT and CTCAE grade, including the number and percentage of subjects experiencing events.

An overview of AEs by treatment group will be provided, including number of subjects experiencing TEAEs, drug related TEAEs, serious TEAEs, drug related serious TEAEs, TEAEs leading to discontinuation of study medication, drug related TEAE leading to discontinuation of study medication, TEAEs leading to death,. The summary will also be provided for subgroups age group (< $60, \ge 60$ years), gender and race.

Imputation of partial dates of AE record is described in Appendix 2 Partial Date Conventions.

[name] S.A	
Protocol RI-01-006	Statistical Analysis Plan

A by-subject listing of all AEs will be provided by treatment group and will include AE term (SOC, PT, and Verbatim term), start date/time and corresponding study day, end date/time and corresponding study day, severity, infusion related reaction (yes/no), relationship, action taken, outcome, seriousness including criteria of serious adverse event (SAE).

4.11.2.1 Analysis of Pre-Treatment AEs

A pre-treatment AE is defined as any AE with an onset date before the date of first administration of study treatment.

A summary of the number of subjects with pre-treatment AEs by SOC, PT a including the number and percentage of subjects experiencing events will be provided.

4.11.2.2 Analysis of Treatment-Emergent Adverse Events

A summary of the number of subjects with drug related TEAEs by SOC, PT including the number and percentage of subjects experiencing events, separately. TEAEs with incidence by $PT \ge 5\%$ in either of DRL_RI or MabThera treatment group will be additionally summarized by SOC, PT and CTCAE grade by treatment group.

A summary of TEAEs observed, based on the onset date, during the rituximab induction and maintenance will be summarized separately by treatment groups.

4.11.2.3 Analysis of TEAEs by Severity

A summary of the number and percentages of subjects with TEAEs, number of events will be provided by SOC, PT and by CTCAE grade including the number and percentage of subjects experiencing events. If same event occurred more than once in the same subject, the highest severity grade will be used for the analysis.

4.11.2.4 Analysis of TEAEs by Relationship

A summary of the number and percentages of subjects with TEAEs, number of events will be provided by SOC, PT and by relationship (not related, related, not applicable) including the number and percentage of subjects experiencing events.

4.11.2.5 Analysis of TEAEs by Outcome

A summary of the number of subjects with TEAE outcome into "Not recovered/Not resolved", "Recovered/Resolved with sequelae/resolved with sequelae", "Recovering/Resolving", "Fatal", and "Unknown" categories for number of events by treatment group will be provided.

4.11.2.6 Analysis of TEAEs Leading to Discontinuation of Study Medication

A summary of the number of subjects with TEAEs leading to discontinuation of study medication by SOC, PT including the number and percentage of subjects experiencing events will be summarized by treatment group.

A by-subject listing of TEAEs leading to discontinuation of study medication will be provided.

